CCT	Cancer Clinical Trial
STM	Saint Thomas More
LCRB	Latine Community Review Board
CHW	Community Health Workers
IRB	Institutional Review Board
PHI	Private Health Information
RCMU	Research Coordination & Management Unit
UNC	University of North Carolina
PI	Primary Investigator
RIS	Research Information Sheet
CTS	Clinical Translational Science

PROTOCOL SYNOPSIS

Study Title	A Colorectal Cancer Educational Intervention in the Latino Community Assessing the Feasibility of Recruitment & Retention via a Church-Based Approach: Identification of Novel Barriers to Cancer Clinical Trial Enrollment
Funder	NCTraCS
Clinical Phase	N/A
Study Rationale	Cancer is the leading cause of death in the US Latino community, with CRC accounting for 10% of overall Latino mortality. Although Latino individuals are among the largest and fastest growing communities of color in the US, currently comprising 18.7%, their representation in CCTs remains low. This is of concern because: 1) advances arising from trials with limited Latino representation may not be applicable to the Latino population, and 2) decreased Latino participation in CCTs may delay Latino access to novel therapies. We believe that low cancer-specific health knowledge may be impacting Latino representation and willingness to participate in CCTs and can be addressed through culturally and linguistically appropriate community-based educational interventions. Since Latino CCT underrepresentation is likely to be a multifaceted phenomenon with potential contributing barriers at the physician-, healthcare system-, and patient-level, understanding the multiple driving forces and barriers is essential to identifying potential targets for improvement and addressing our CTS roadblock of Latino underrepresentation in CCTs.
Study Objective(s)	
1. To identify novel Latino-perceived barriers to participation in CCTs.2. To assess the impact that CRC educational videos in Spanish have on participants' CRC knowledge.3. To assess the potential relationship between an increase in health knowledge of a specific cancer via educational videos in Spanish and willingness to participate in CCTs.
Test Article	The intervention in this study entails three CRC educational videos in Spanish.
Study Design	To achieve our goals, Spanish speaking Latino individuals will be recruited to participate in an educational intervention that will take place at STM Church. On Study Day 1, participants will be given the CRC Knowledge Survey in Spanish before watching three CRC educational videos. After watching the videos, participants will be given the Post Video CRC Knowledge Survey . After 30 +/- 7 days, participants will be asked to return to the Church for Study Day 2 in order to complete the 30 Day Follow Up CRC Knowledge Survey ,

consisting of the original survey plus an open-ended question regarding barriers to participation in CCTs. Subsequently, 20 participants will be invited to participate in one-on-one qualitative interviews aimed at gaining further insight on Latino-perceived barriers to CCT participation. (Study Day 3)

Subject Population

Participants should:

Key Criteria for Inclusion and Exclusion:

1. Self-identify as Hispanic/Latino.
2. Be Spanish speakers.
3. Be 18 years or older.

Participants will be excluded if they:

1. Do not identify as Hispanic/Latino.
 2. Are not Spanish speakers.
 3. Are younger than 18 years old.
-

Number Of Participants

60

Study Duration

Every participant’s involvement will require at least two and a half hours over a 4-month period (two hours to take the *CRC Knowledge Survey*, watch the videos and take the *Post Video CRC Knowledge Survey* and thirty minutes to complete the *30 Day Follow Up CRC Knowledge Survey*). Participants willing to take part in a qualitative one-on-one interview will be asked to participate for an additional hour, totaling three and a half hours over a 6-month period. The entire study is expected to last 12 months.

Study Phases

A. Educational Video:

A. Educational Video

i. Screening

(i) Screening: Spanish speaking attendees at STM Church will be screened for study eligibility.

ii. Study Intervention

(ii) Intervention (Study Day 1): Consented participants will complete the *CRC Knowledge Survey*, watch three CRC educational videos and complete the *Post Video CRC Knowledge Survey*. Both surveys will be administered on paper form.

iii. Follow-Up

B. Identification of Barriers Preventing Latinos from participating in CCTs

(ii) Follow up (Study Day 2): In order to assess retention of knowledge, participants will return to STM Church 30 +/- 7 days after Study Day 1 to complete the *30 Day Follow Up CRC Knowledge Survey* on paper form.

B. Identification of Barriers for Latino Participation in CCTs:

(Study Day 3): 20 of the participants will be asked to participate in a qualitative one-on-one interview aimed at identifying barriers preventing Latinos from participating in CCTs.

Efficacy Evaluations

Participants’ knowledge on CRC symptoms, risk factors, and general CRC facts will be assessed using questions from the “Bowel Cancer Awareness Measure” and from the “Colorectal Cancer Screening Decision Quality Instrument (CRC-DQI)”.


Safety Evaluations
 <hr/> 
Statistical And Analytic Plan
	
N/A, this study imposes minimal risk.
 <hr/> 
A. Identification of Barriers: The top 2 conceptual themes within each section of the interview (attitudes regarding general clinical trials, attitudes regarding CCTs, and perception of the Hispanic/Latino community) and the top 3 higher-level, holistic themes across the sections will be reported in terms of percentage of participants.
 
B. Assessment of the potential impact of the educational videos in Spanish on CRC knowledge: Use of repeated measures ANOVA with appropriate follow-up contrasts to compare total number of correct responses within three time points (baseline vs post-video; baseline vs 30 +/- 7 days follow up; post-video vs 30 +/- 7 days follow-up) accounting for multiple observations within participants.
 
C. Exploration of the potential relationship between an increase in health knowledge of a specific cancer via educational videos in Spanish and willingness to participate in CCTs: Since questionnaires will be completed pre- and post-video, we will explore, in a preliminary fashion, the association between watching the video (X) and willingness to participate in CCTs (Y) using repeated-measures/mixed-effects logistic regression on the paired responses of participants. The mediating effect of Study Day 1 post-video health knowledge levels (M) on the relationship between X and Y (established in the preliminary step above) will be explored. Using a structural equation modeling approach, two mixed-effects generalized linear models will be carried out: one model uses both X and M to predict Y, while another uses only X to predict M. The two models will be compared and tested using the algorithm introduced by Imai and colleagues. The estimated average causal mediation effect (from X to Y, through M) will be tested using the bootstrapping method with 1,000 replications, and the proportion of the effect being mediated will be reported as the effect size. Lastly, in order to explore an adjusted approach, the same steps used for the mediation model will be replicated, while incorporating demographic variables as covariates.

--	---


DATA AND SAFETY MONITORING PLAN
	
Monitoring of quality data entry will be performed by our collaborators at the RCMU and members of the study team after the initial 5 registrants and then after every 10. The PI will be responsible for data monitoring. To minimize the risk of breach of confidentiality, all PHI will be stored in a password protected server accessible only by members of the study team. To minimize the risk of emotional distress, participants will be reassured that they will not have to answer any questions that make them feel uncomfortable and may stop completing the questionnaires at any point.

---	--

BACKGROUND AND RATIONALE

1.1 Introduction

Cancer is the leading cause of death in the US Latino community, with CRC accounting for 10% of this overall mortality.¹ Although Latino individuals are among the largest and fastest growing communities of color in the US, currently comprising 18.7%,² their representation in CCTs remains low.³⁻⁵ This is of concern because: 1) advances arising from trials with limited Latino representation may not be applicable to the Latino population,⁶ and 2) decreased Latino participation in CCTs may delay Latino access to novel therapies.

We believe that low cancer-specific health knowledge may be impacting Latino representation and willingness to participate in CCTs and that this can be addressed through culturally and linguistically appropriate community-based educational interventions.^{7,8} Since Latino CCT underrepresentation is likely to be a multifaceted phenomenon with potential contributing barriers at the physician-, healthcare system-, and patient-level, understanding the multiple driving forces and barriers is essential to identifying potential targets for improvement and addressing our CTS roadblock of Latino underrepresentation in CCTs.

1.2 Name and Description of Investigational Product or Intervention

This study will assess the impact of three educational videos in Spanish on participants' CRC knowledge and willingness to participate in CCTs.

1.3 Non-Clinical and Clinical Study Findings

Potential benefits from participation in this study may include improvement in participants' knowledge of CRC, a major healthcare problem for the Latino community. The pre- (*CRC Knowledge Survey*) and post-educational video (*Post Video CRC Knowledge Survey*) questionnaires will allow us to determine the impact of the educational videos on CRC knowledge and retainment as well as allow us to explore the potential relationship between an increase in knowledge on a specific cancer and willingness to participate in CCTs. The follow-up questionnaire (*30 Day Follow Up CRC Knowledge Survey*) will assess retention of information at 30 +/- 7 days. In addition, through the conduct of qualitative one-on-one interviews, Latino-perceived barriers to CCT participation may be identified. The study requires completion of three questionnaires and a potential one-on-one interview. It will be conducted in a familiar location (namely, STM Church), and we do not anticipate any adverse events. There is minimal risk of emotional distress from answering questions related to CRC. However,

participants will be encouraged to not answer any questions that make them feel uncomfortable and to stop the questionnaires at any point. Participants will be asked to provide contact information in order to schedule interviews. Efforts are in place to minimize any potential breach of confidentiality. Overall, the potential risks from participating in our study are minimal while the knowledge to be gleaned, including Latino-specific barriers to CCT participation, will be significant.

1.4 Relevant Literature and Data

Use of the Church-based Approach: Approximately 75% of Foreign- and 55% of US-born Latino identify as Christian, respectively⁹ and 74% of Latinos attend Church at least 1-2 times a month.¹⁰ As a testament to the important role that the Church plays in the Latino community, several interventions have been evaluated in the Church setting¹¹⁻²⁵ including: breast cancer prevention;^{16,17,19} diabetes mellitus;^{14,23,24} cancer screening promotion;^{13,15} physical exercise promotion;^{18,21} HIV stigma reduction;²⁰ stroke prevention;²² organ donation promotion;²⁵ and cardiovascular risk reduction.^{11,12} With the exception of a recent study limited to Latino men,²⁶ we are not aware of any Church-based educational interventions that have: 1) educated Latinos on CRC or 2) reported strategies for their recruitment and retention. We believe that our approach, if successful, may have broad applicability for the recruitment of other ethnic minority groups with high religious beliefs across a multitude of denominations (e.g. 68% of Asians attend Church at least 1-2/month¹⁰).

Education of the general population/non-cancer afflicted individuals: Most CCT educational interventions target individuals afflicted with the disease.²⁷⁻³³ While only a handful target the non-affected general population,³⁴⁻³⁷ this approach may be uniquely suited for recruitment of Latinos in CCTs since in the Latino community the decision to enroll in a CCT is likely to be multifactorial and heavily influenced by input from family members.³⁸ In fact, a core value of Latino culture is *familismo*: “the concept of a broad network of familial support that extends beyond the nuclear family”.³⁹ Since lack of family support may act as a barrier to Latino CCT participation,^{40,41} we believe that: (1) educating the general population and non-cancer afflicted Latino individuals and families will facilitate Latino CCT participation and (2) the Church setting, given the multiple familial generations attending mass, is a viable venue for educating the Latino general population.

Education on a specific cancer & willingness to participate in CCTs: Unlike other studies aimed at increasing willingness to participate in CCTs solely through general education about CCTs, our study focuses primarily on education on a specific cancer.^{27-37,42} Since education on CRC has been shown to

increase willingness to participate in CRC screening,⁴³ we anticipate it could similarly increase willingness to participate in CCTs. This can be achieved by increasing awareness of CRC and its treatment options ultimately leading to improved decision-making.²⁷

Questionnaire: Knowledge on CRC and willingness to participate in CCTs will be assessed using 3 subscales from 2 CRC knowledge questionnaires previously validated in English. [name] and [name] from the Odum Institute combined the 3 subscales^{44–46} to form our Pilot Study Questionnaire. This Pilot Study Questionnaire has been translated into Spanish by Language Line Solutions, hired through the UNC Clinical Research Support Office (CRSO), and revised, using an iterative process with input from the LCRB, for linguistic and cultural relevance and accuracy. The resultant Pilot Study Questionnaire consists of 29 items that assess health knowledge levels and 1 that assesses willingness to participate in CCTs (30 total questions). General knowledge on CRC will be assessed using the prompted 9-item “Awareness of warning signs” (Yes/No) and the prompted 11-item “Awareness of risk factors” (5 point Likert agreement scale) subscales of the “Bowel/CRC Cancer Awareness Measure (Bowel/CRC CAM)”.⁴⁵ Specific knowledge on CRC screening will be assessed using the 9-item “Knowledge on CRC screening” (mixed types of response options) subscale from the CRC Screening Decision Quality Instrument (CRC-DQI).⁴⁶ Our outcome variable, *willingness to participate in CCTs*, will be assessed using a “Yes/No” item.^{28,36,42} Our Pilot Study Questionnaire is used in all three surveys, namely the *CRC Knowledge Survey; Post Video CRC Knowledge Survey and 30 Day Follow Up CRC Knowledge Survey*. Additionally, the *CRC Knowledge Survey*, administered pre-video, includes seventeen questions capturing demographic information (47 total questions), while the *30 Day Follow Up CRC Knowledge Survey* contains in addition to the pilot study Questionnaire, an open-ended question aimed at capturing barriers preventing Latinos from participating in CCTs (31 total questions).

Video: Previous studies demonstrate the superiority of a video-based approach compared to other educational tools in terms of knowledge acquisition and acceptance within the Latino population.^{42,43,47,48} Based upon strong recommendation from the UNC’s Audio and Video Production Team, we contracted DWALT Media, which has filmed videos for UNC Medical Center and worked with local churches, for the production of our Spanish educational videos. Filming occurred at UNC Medical Center and included animations, figures and 3D models. The videos will educate the participants on CRC symptoms, risk factors, screening and CRC facts. In addition, the third video will contain some information regarding CCTs. Since Latinos consider physicians a trustworthy source of

medical information,⁴⁹ our PI, a member of the STM Latino community, will present some of the educational material.

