2.3 Study Population

Participants should:

- (1) Self-identify as Hispanic/Latino.
- (2) Be Spanish speakers.
- (3) Be 18 years or older.

Participants will be excluded if they:

- (1) Do not identify as Hispanic/Latino.
- (2) Are not Spanish speakers.
- (3) Are younger than 18 years.

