3 STUDY PROCEDURES

3.1 Screening/Baseline Visit procedures

Interested participants will be asked to complete an Intake Form in Spanish which captures name and contact information as well as determines study eligibility as listed above. Those deemed eligible will be prompted to complete the RIS. In addition to in-person recruitment, interested participants will have the opportunity to complete the Intake Form using our study website, which will be readily accessible via a QR code found on the Study Flyer.

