4.4 Methods

Primary Endpoint: Twenty enrolled participants will participate in qualitative, semi-structured, one-on-one interviews that will be performed in Spanish. The interviews will be recorded and transcribed.

ATLAS.ti software will be used for the transcript analysis. The top 2 conceptual themes within each section of the interview (attitudes regarding general clinical trials, attitudes regarding CCTs, and perception of the Hispanic/Latino community) and the top 3 higher-level, holistic themes across the sections will be reported in terms of percentage of participants.

Secondary Endpoint 1: Use of repeated measures ANOVA with appropriate follow-up contrasts to compare total number of correct responses within three time points (baseline vs post-video; baseline vs 30 +/- 7 days follow-up; post-video vs 30 +/- 7 days follow-up) accounting for multiple observations within participants. Knowledge pertaining to CRC symptoms will be assessed using the “Knowledge of Warning Signs” questions from the “Bowel Cancer Awareness Measure”. Potential answers include “Yes”, “No” and “Don’t Know”. The overall score will range from 0 to 9 and it is anticipated that average scores will increase after the intervention. Higher scores imply a greater knowledge of symptoms.

Secondary Endpoint 2: Use of repeated measures ANOVA with appropriate follow-up contrasts to compare total number of correct responses within three time points (baseline vs post-video; baseline vs 30 +/- 7 days follow-up; post-video vs 30 +/- 7 days follow-up) accounting for multiple observations within participants. Knowledge pertaining to CRC risk factors will be assessed using the “Knowledge of Risk Factors” questions from the “Bowel Cancer Awareness Measure”. This scale is measured using a Likert 1-5 scale with “1” corresponding to “Strongly Disagree” and “5” corresponding to “Strongly Agree”. The overall score will range from 11 to 55 and it is anticipated that the average scores will increase after the intervention. Higher scores imply higher knowledge of risk factors.

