4.5 Sample Size and Power

A traditional “power analysis” is not directly applicable to the primary endpoint of the study which is qualitative in nature. Based on published methodologies to assess the adequate sample to reach “saturation”,⁵²⁻⁵⁴ we chose to invite 20 participants for qualitative interviews.

For our quantitative, secondary endpoints, a traditional “power analysis” was performed. A total of 60 participants will be recruited into the study. If in our study population the mean difference is 0.4, which as defined by Cohen is a small to medium difference, and the pre- to post- correlation is 0.5, then the power to reject the null hypothesis will be over 80%. If the differences in our study population are more extreme, our sample size will have even more power to reject the null hypothesis.

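### The analyses of endpoints 1–4 make no allowance for relatives who enrol together; if relatives' changes are alike, the standard errors will be too small

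*Combined protocol and SAP*

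**What the plan says.** **Setting.** Section 1.4 (Relevant Literature and Data) supports the choice of venue partly on family grounds: the Church, "given the multiple familial generations attending mass, is a viable venue". The same paragraph wants families as well as individuals to be educated, and says that relatives weigh heavily in a decision to join a cancer trial.

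**Who may enrol.** Section 2.3 asks that participants "Self-identify as Hispanic/Latino", speak Spanish and be adults. Section 6 enrols eligible people consecutively. Neither section limits enrolment to one member of a household.

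**What is recorded.** Section 3.1 states: "Interested participants will be asked to complete an Intake Form in Spanish which captures name and contact information", and that the form determines eligibility. Section 9 adds demographics for the website version. Section 1.4 mentions seventeen demographic questions, which are not reproduced. No household number is described.

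**Analysis.** For endpoints 1–3, section 4.4 plans repeated-measures ANOVA "accounting for multiple observations within participants". For endpoint 4 it plans mixed-effects logistic regression on each participant's paired responses, then a mediation analysis with 1,000 bootstrap replications. It does not state the resampling unit. No family term, clustered standard error or household bootstrap appears.

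**Power.** Section 4.5: "A total of 60 participants will be recruited into the study". It continues: "If in our study population the mean difference is 0.4" and "the pre- to post- correlation is 0.5", "then the power to reject the null hypothesis will be over 80" per cent. There is no design effect.

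**The concern.** The venue was chosen partly because families attend it, and the rules let relatives join. Co-enrolment is therefore foreseeable, although how common it will be cannot be known from the documents. Relatives watch the same videos, may start from similar knowledge on bounded scales, and may talk about the content before Study Day 2. The plan's own rationale also expects family influence on willingness, which is the outcome of endpoint 4.

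If relatives' changes resemble one another, 60 participants carry less information than 60 unrelated people. The planned tests would then reject a true null too often and the intervals would be too narrow. An analysis that allowed for the clustering would have less power than section 4.5 implies. Without a household identifier, a reader could not readily tell whether this had happened.

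**Working it through.** **Inputs from section 4.5:** n = 60; difference 0.4, read as a standardised difference because Cohen is cited; pre-post correlation 0.5; stated power over 80%.

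**Assumptions, because the documents are silent:** two-sided alpha 0.05, no dropout, m enrolees per household, and ICC of relatives' change scores.

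**Step 1, the plan's figure.** The SD of change in baseline SD units is sqrt(2 × (1 − 0.5)) = 1, so the standardised mean change is 0.4/1 = 0.4. A paired t-test on 60 independent participants (noncentral t) has power 86.2%. The stated figure of over 80% is reproduced. The smallest n giving 80% is 52.

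**Step 2, effect of clustering.**
- Design effect DE = 1 + (m − 1) × ICC.
- The true standard error is sqrt(DE) times the one that the planned test uses.
- Type I error of the planned test = 2 × (1 − Φ(1.96/sqrt(DE))).
- Power of a correctly clustered test is approximated by the paired t-test at effective n = 60/DE.

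| m | ICC | DE | SE ratio | Effective n | Type I error, planned test | Power, clustered test |
|---|---|---|---|---|---|---|
| 1 | any | 1.00 | 1.00 | 60 | 5.0% | 86.2% |
| 1.25 | 0.05 | 1.0125 | 1.01 | 59.3 | 5.1% | 85.7% |
| 2 | 0.1 | 1.10 | 1.05 | 54.5 | 6.2% | 82.7% |
| 2 | 0.3 | 1.30 | 1.14 | 46.2 | 8.6% | 75.8% |
| 3 | 0.3 | 1.60 | 1.26 | 37.5 | 12.1% | 66.4% |

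Worked row: m = 2, ICC = 0.3. DE = 1 + 1 × 0.3 = 1.3; 1.96/sqrt(1.3) = 1.719; 2 × (1 − Φ(1.719)) = 8.6%; 60/1.3 = 46.2.

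The formula assumes equal household sizes. An average of 1.25 must mix sizes: 36 singles and 12 pairs make 60 people in 48 households. Then DE = 1 + ((36 × 1 + 12 × 4)/60 − 1) × 0.05 = 1.02, still negligible.

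**Step 3, break-even.** A clustered test keeps 80% power while 60/DE is at least 52, that is, DE up to 60/52 = 1.15. With pairs throughout, this is an ICC of about 0.15.

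**Step 4, simulation.** The planned paired t-test, simulated with correlated relatives, gave type I error 8.4% (m = 2, ICC 0.3) and 12.1% (m = 3, ICC 0.3), in line with the formula. A family effect that is constant over time gave 5.0%, so it causes no inflation in the pre-post contrasts.

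**Step 5, mediation.** In the model that predicts willingness from video and knowledge, the knowledge coefficient draws partly on differences between people. Stable family similarity does not cancel there. If the bootstrap resamples participants, it will not reflect that similarity. The documents give too little to put a number on this.

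**The case against.** Four fair points can be made in favour of the plan.

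1. *Recruitment is of individuals.* A reader might infer from the venue argument that families leaving Mass together are the target. The documents do not support that. Flyers go to attendees in general, each person is screened by Intake Form, and the sentence about generations is background on the venue. This stands; co-enrolment is possible and foreseeable, not designed.

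2. *Co-enrolment alone does no harm to the pre-post contrasts.* This also stands. Shared language or schooling cancels if its effect is constant over time. Inflation needs correlated changes, for which the documents give no evidence. Talk at home between visits can reach only the contrasts involving the 30-day survey, because the pre- and post-video surveys are both completed on Study Day 1. Correlated learning gains and the mediation path remain.

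3. *The problem might be repairable later.* A reader might infer that household can never be recovered. That goes too far: names, contact details and dates of birth are handled, and the demographic items are not shown. The supportable statement is that no household identifier is described and no analysis uses one.

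4. *The power loss is not a property of the planned test.* Correct. In simulation the uncorrected test still rejects in 79.8% to 85.1% of trials for m of 2 or 3 and ICC of 0.1 to 0.4. It does so partly because its standard error is too small, so that rejection rate comes with an inflated type I error. The lower powers in the table belong to a test that holds its level.

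**Conclusion.** The point holds as a conditional one, for the secondary endpoints only. The plan permits relatives to enrol, describes no means of identifying them, and models correlation only within a participant. If relatives enrol and their changes are positively correlated, the standard errors are too small.

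The size rests wholly on assumed household sizes and ICCs. Type I error runs from 5.1% (1.25 per household, ICC 0.05) through 8.6% (2, ICC 0.3) to 12.1% (3, ICC 0.3). Averages of 2 or 3 would require co-enrolment to be very common, so the low end deserves equal attention, and there almost nothing changes. The documents do not support saying that the standard errors will be wrong, only that they may be. The primary endpoint is qualitative and has no standard error, and endpoint 4 is explored in a preliminary way. This is a low-cost improvement, not a flaw that threatens the study.

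**What to change.** - **Intake Form (3.1, 9):** add an item asking whether another household member is enrolled, and assign a household number.
- **Section 4.4, endpoints 1–4:** use household-clustered standard errors with a small-sample correction, with participants nested within household.
- **Section 4.4, mediation:** state the bootstrap's resampling unit and make it the household.
- **Reporting:** give the number of households beside the number of participants.

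The cost is one form item, one model option and slightly wider intervals if relatives co-enrol. If none do, results are essentially unchanged and the study can show that its participants came from separate households.
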